### 7. STATISTICAL CONSIDERATIONS

### 7.1. REFERENCE START DATE AND STUDY DAY

Study Day will be calculated from the reference start date and will be used to show the start/ stop day of assessments and events.

Reference start date is defined as the date of the first dose of study medication (Day 1 is the study day of the first dose of study medication).

• If the date of the assessment or event is on or after the reference start date then:

Study Day = (date of assessment or event - reference start date) + 1.

• If the date of the assessment or event is prior to the reference start date then:

Study Day = (date of assessment or event – reference start date).

Document:	\\quintiles.net\enterprise\Apps\sasdata\SASa\sas\Sunovion\ 363856\BZA44200\Biostatistics\Documentation\SAP\V1\SE	SEP- P361-301 SAP Final '	V1.0_26JUL2023
Author:		Version Number:	Final 1.0
		Version Date:	26JUL2023
Template No.	CS_TP_BS016 Revision 5	Reference: (	CS_WI_BS005

Effective Date: 01Apr2018

In the situation where the assessment or event date is partial or missing, Study Day and any corresponding durations will appear missing in the listings. Partial assessment or event dates will however be presented as is in the listings.

### 7.2. **BASELINE**

Unless otherwise specified, baseline is defined as the last non-missing measurement taken prior to the first dose of study medication (including unscheduled assessments). Whenever available, the time information should be accounted for in the derivation of baseline values. In the case where time is not available and the date of the last non-missing measurement and the date of the first dose of study medication coincide, that measurement will be considered baseline.

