q Unscheduled BARS, AIMS, and SAS scales should be administered if a subject develops extrapyramidal symptoms (EPS) requiring treatment.

r All adverse events occurring after signing informed consent through the end of study will be collected.

s PANSS, BNSS, MADRS, CGI-S, and C-SSRS to be completed on Day -2 or Day -1.

t BARS, AMES, SAS to be collected on Day -1 or Day 1 (predose).

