### **11.6.3. Vital Signs**

Vital sign measurements consist of systolic and diastolic blood pressures, respiratory rate, pulse rate, and oral temperature.

Blood pressure and pulse rate should first be taken with the subject in the supine position after resting for  $\geq 5$  minutes. Blood pressure and pulse rate will be taken again after standing for 2 to 4 minutes. The same arm should be used during each assessment of blood pressure and pulse rate throughout the study. If a subject develops symptoms consistent with orthostatic hypotension (light-headedness, dizziness, or changes in sensorium upon standing) at any point, his or her supine and standing blood pressure and pulse rate should be collected at that time in the manner described above. Vital signs results assessed as clinically significant by the investigator will be reported as adverse events. Vital signs will be obtained prior to clinical laboratory collection and performance of an ECG.

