# 7.3. RETESTS, UNSCHEDULED VISITS AND EARLY TERMINATION DATA

In general, for by-visit summaries, data recorded at the nominal visit will be presented.

In the case of a retest, the assessment recorded under the planned visit will be used for by-visit summaries, and the assessment(s) recorded under unscheduled visit(s) will be presented in listings only.

Early termination data will be mapped to the next scheduled or planned timepoint where an assessment is expected to be performed as specified by the Schedule of Assessment table in the Protocol for by-visit summaries. This applies to all efficacy, safety, and PK data.

Listings will include scheduled, unscheduled, retest and early discontinuation data.

Unscheduled measurements will not be included in by-visit summaries. Unscheduled measurements collected prior to the first dose of study medication will contribute to the derivation of the baseline value. Unscheduled measurements collected post baseline will contribute to the derivation of potentially clinically significant (PCS) post-baseline value and worst case value where required.

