- For summaries by relationship to study drug, TEAEs assessed as "possible," "probable," or "definite" will be grouped as "related." If a subject reports more than one TEAE within the same treatment regimen, SOC and PT, and any are related, it will be summarized as related. Any TEAE with a missing relationship to study medication will be regarded as "related" to study medication.
- For summaries by dose at AE onset, TEAEs will be summarized by the last actual dose level the subject was on before the onset of event. If a subject reports more than one TEAE within the same dose level, SOC and PT, it will be counted only once.

Untoward medical occurrences that occur between the time of signing the ICF and first drug administration are pre-treatment events.

A listing of AEs (TEAEs and pre-treatment events), as well as a listing of Serious TEAEs, TEAEs leading to discontinuation of study medication and discontinuation from study, TEAEs of potential drug abuse and dependence (see APPENDIX 6), and a listing of treatment emergent deaths will be presented.

See APPENDIX 2 for handling of partial dates for AEs. In the case where it is not possible to determine whether an AE began before or after dosing, the AE will be classified by the worst case; i.e. treatment emergent.

Document:	ocument:         \\quintiles.net\enterprise\Apps\sasdata\SASa\sas\Sunovion\SEP-           363856\BZA44200\Biostatistics\Documentation\SAP\V1\SEP361-301         SAP Final V1.0_26JUL:					
Author:		Version Number:	Final 1.0			
		Version Date:	26JUL2023			
Template No.:	CS_TP_BS016 Revision 5	Reference: C	S_WI_BS005			

Effective Date: 01Apr2018

Presentations regarding each of the categories described in the sub-sections below, will be provided as described and specified in the templates.

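### SAP 7.2 lets an untimed, symptom-triggered Day 1 rating become baseline; the clear case is an unscheduled BARS, AIMS or SAS after the first dose when the planned rating was done on Day -1

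*SAP*

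**What the plan says.** SAP 7.2 defines baseline as the last non-missing value before the first dose and makes unscheduled assessments eligible. It then says: "Whenever available, the time information should be accounted for in the derivation of baseline values". For a missing time it gives a tie-break: if "the date of the last non-missing measurement and the date of the first dose of study medication coincide, that measurement will be considered baseline". The tie-break makes no distinction between scheduled and unscheduled readings.

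SAP 7.3 adds: "Unscheduled measurements collected prior to the first dose of study medication will contribute to the derivation of the baseline value". Unscheduled post-baseline readings go to the PCS and worst-case derivations and stay out of by-visit summaries. Section 7.3 does not say where an untimed unscheduled Day 1 reading belongs.

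Protocol 11.9.2.3 places Day 1 procedures before dosing unless otherwise specified. Footnote t of the Schedule of Assessments lets the planned BARS, AIMS and SAS be done on Day -1 or predose on Day 1. Footnote q adds: "Unscheduled BARS, AIMS, and SAS scales should be administered if a subject develops extrapyramidal symptoms (EPS) requiring treatment". Protocol 11.6.3 has a similar trigger for orthostatic symptoms at any point in the study, when "his or her supine and standing blood pressure and pulse rate should be collected at that time in the manner described above".

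For adverse events the SAP resolves uncertain timing the other way. Under SAP 16.1, "where it is not possible to determine whether an AE began before or after dosing, the AE will be classified by the worst case", which means treatment emergent.

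**The concern.** A same-day default to baseline is reasonable when the planned assessment is predose. An unscheduled rating made because symptoms appeared has no such presumption. Morning dosing is recommended, so most of Day 1 follows the dose.

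If such a rating is taken as baseline, a possible first-dose effect moves to the pre-treatment side of the comparison. Later values are then measured against an already raised score. Whether adjunctive treatment is associated with extrapyramidal symptoms on these three scales is a stated safety objective, so the error would fall on summaries that serve it. The baseline table in SAP Section 10, which reports AIMS total, BARS total and SAS mean score, would carry the same value.

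The SAP would also disagree with itself. An untimed Day 1 akathisia event is treatment emergent under SAP 16.1 and Appendix 2, while the untimed rating of that akathisia would be the pre-treatment baseline.

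**Working it through.** The plan states no figure on this point to reproduce. The check applies the SAP's own rules under both candidate baselines. All readings below are assumed for illustration; none comes from the documents.

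**Conditions for the clear case.** All four are needed: the planned scales were done on Day -1; EPS requiring treatment appeared after dosing on Day 1; an unscheduled rating was made that day; and no clock time was entered. The unscheduled rating is then the only Day 1 value and so the last non-missing one.

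**Size of the error.** Let P be the true predose score, U the untimed Day 1 rating and W the Week 2 score.
- True change = W - P. Change under the rule = W - U. Error = (W - U) - (W - P) = P - U.
- On these scales a higher score is worse, so the error points toward improvement whenever U is greater than P.

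**BARS global class** (SAP 16.7: higher than baseline is worsened, lower is improved). P = 0, U = 3, W = 1.
- Baseline P: 1 - 0 = +1, worsened.
- Baseline U: 1 - 3 = -2, improved.
- One reclassified subject is 1/22 = 4.5% of the planned sample, or 1/16 = 6.3% of 16.

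**BARS total, mean change.** P = 0, U = 4, W = 2.
- Baseline P: 2 - 0 = +2. Baseline U: 2 - 4 = -2. Error = -4.
- Effect of one such subject on the mean change: -4/22 = -0.18, or -4/16 = -0.25.

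**AIMS and SAS shifts.** If the score is normal on Day -1, abnormal on the untimed Day 1 rating and abnormal at Week 2, the shift changes from normal-to-abnormal to abnormal-to-abnormal. The AIMS global severity class uses the same comparison as the BARS global and can flip in the same way.

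**Vital signs.** Footnote t does not cover these, and SAP 16.4 lists a Day 1 predose reading. Two Day 1 readings therefore exist, and if one or both lack a time the SAP gives no way to say which is last. Take supine systolic pressure of 120 predose, 88 unscheduled and untimed, and 88 at Week 2. PCS-low needs a value of 90 or less and a fall of at least 20 (SAP 16.4.1).
- Baseline 120: 88 - 120 = -32, PCS-low met.
- Baseline 88, if that reading is chosen: 88 - 88 = 0, PCS-low not met.

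**Orthostatic hypotension** (SAP 16.4.2). The definition compares standing with supine at the same timepoint. Supine 110 and standing 88 give a fall of 22, which meets the 20 mmHg limit whichever baseline is used.

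**The case against.** The strongest reply is that the SAP does not tell anyone to use a post-dose reading. Section 7.2 opens by requiring a value taken before the first dose, times must be used when they exist, and 7.3 admits only unscheduled readings collected before the first dose. A rating known to follow dosing fails both tests. This has force: the defect is an unresolved corner case, not an instruction to use post-dose data. It does not remove the defect, because the labels in 7.3 presuppose the timing that is missing. The only sentence that addresses an untimed Day 1 reading is the tie-break, and a programmer would apply it.

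Several other objections stand:
- Neither document says that clock times are missing for scales or vital signs, nor that they are recorded, so no frequency can be given.
- The event itself is not hidden. New symptoms are recorded as AEs, AEs of uncertain order count as treatment emergent, and all scale and vital-sign data are listed.
- The overall post-baseline periods in SAP 16.4 and 16.7 include unscheduled visits occurring after the first dose, without reference to the baseline label. Loss of the reading from those summaries is possible but not established.

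A reader might infer that any untimed Day 1 measurement becomes baseline, that a first-dose orthostatic reading is subtracted out, or that the error always favours the drug. The documents support none of these. Only the last non-missing reading qualifies, and only without a time. Orthostatic hypotension involves no baseline. And every subject takes a background antipsychotic, so an unscheduled Day 1 rating could be genuinely predose; a repeat after recovery could also be the last value.

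**Conclusion.** The point holds in a narrow form. For BARS, AIMS and SAS, when the planned rating was on Day -1 and an untimed unscheduled rating follows the first dose on Day 1, the tie-break yields a wrong baseline. It can bias change, the BARS and AIMS global classes, and the AIMS and SAS shifts toward unchanged or improved. For vital signs the wording is ambiguous: change from baseline and PCS flags could be affected, but the orthostatic hypotension definition is not.

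Per affected subject the effect is one reclassification, 4.5% of 22, and in the assumed example -0.18 on the mean BARS total change. The number of affected subjects is unknown and probably very low, since four conditions must coincide. The consequence is confined to descriptive safety summaries; the primary PET endpoint is not involved. The conclusion rests on the untimed rating being in fact post-dose and higher than the true predose score.

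**What to change.** Add to SAP 7.2 that the untimed same-day rule applies only to assessments scheduled predose on Day 1, and that an untimed unscheduled assessment dated on the first-dose day is post-baseline unless the record shows it was taken before the dose. This agrees with the worst-case rule in SAP 16.1 and fills the gap left by 7.3. It also settles the vital-sign ambiguity, because only the scheduled predose reading would then benefit from the default.

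The cost is one sentence and a small programming condition, with no new data. The downside is that an untimed unscheduled reading that was in fact predose, but cannot be shown to be so, would be counted as post-baseline.

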# 7.3. RETESTS, UNSCHEDULED VISITS AND EARLY TERMINATION DATA

In general, for by-visit summaries, data recorded at the nominal visit will be presented.

In the case of a retest, the assessment recorded under the planned visit will be used for by-visit summaries, and the assessment(s) recorded under unscheduled visit(s) will be presented in listings only.

Early termination data will be mapped to the next scheduled or planned timepoint where an assessment is expected to be performed as specified by the Schedule of Assessment table in the Protocol for by-visit summaries. This applies to all efficacy, safety, and PK data.

Listings will include scheduled, unscheduled, retest and early discontinuation data.

Unscheduled measurements will not be included in by-visit summaries. Unscheduled measurements collected prior to the first dose of study medication will contribute to the derivation of the baseline value. Unscheduled measurements collected post baseline will contribute to the derivation of potentially clinically significant (PCS) post-baseline value and worst case value where required.

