#### **Open-Label Treatment Period (2 weeks; Day 1 to Day 14+5 days):**

Treatment: At Visit 2 (Day 1), subjects who continue to meet all study inclusion criteria and none of the exclusion criteria (see below) will begin treatment with SEP-363856 as an adjunct to their background, stable antipsychotic treatment. Study drug dosing will begin on Day 1. Study drug (Days 1 – 13) should be taken approximately the same time each day with morning dosing recommended. Doses may be moved to the evening for reasons of tolerability. The final dose, on Day 14, should occur approximately 2 to 4 hours prior to the final PET scan. Treatment with SEP-363856 will occur once-daily during the treatment period with procedures outlined in [Table 2](#) (schedule of assessments). Subjects will receive SEP-363856 50 mg/day on Day 1 through Day 3. On Day 4, subjects will titrate up to a dose of 75 mg/day. A one-time dose reduction (from 75 mg to 50 mg) for tolerability purposes is permitted and may occur at any time, at the Principal Investigator's discretion. Subjects who have a dose reduction for tolerability will continue to receive the reduced dose for the remainder of the study. Subjects will remain in-clinic and on treatment through Week 2 until all Day 14 assessments including the PET scan are complete. In the event of an unsuccessful PET scan on Day 14, additional days of dosing may be necessary up to, but not exceeding, Day 19. If any such additional days are necessary, subjects will remain in the clinic and continue their usual daily dosing. All Day 14 assessments are to be completed the same day as the PET scan. Subjects will be eligible for clinic discharge at the Week 2 visit, at the Investigator's discretion.

Blood samples for determination of SEP-363856 and SEP-363854 plasma concentrations will be collected on Day 1 (predose), Day 2 (postdose), Day 7 (postdose), and Day 14 (prior to PET scan). Blood samples for antipsychotic plasma concentrations will be collected on Day -2, Day 1 (predose), Day 2 (postdose), Day 7 (postdose), and Day 14 (prior to PET scan). Blood samples for SEP-363856, SEP-363854 and antipsychotic plasma concentrations should be collected at approximately the same time as dosing for Day 2 (postdose) and Day 7 (postdose) while the Day 14 collection should occur immediately prior to the PET scan.

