a Subjects who screen fail may be re-screened up to two times, if judged appropriate by the Investigator. Subjects who screen fail due to MRI or PET or fMRI results may not be re-screened. Screening procedures will occur on multiple days. If subject re-screened, an MRI (without any abnormality) obtained at the study's imaging center within 90 days prior to Day -1 check-in is acceptable for eligibility.

b Extension of in-clinic stay during the screening phase to complete screening assessments may be allowed on a case-by-case basis with pre-approval of the Medical Monitor. Subject must be admitted to the clinic by Day -2.

c Dispensation of study drug on Day 1 and Day 8. All study drug will be taken once daily by mouth from Day 1 through Week 2 (Day 14). After 3 days of treatment with 50 mg/day SEP-363856, subjects are required to titrate up to 75 mg/day. Subjects may dose reduce one time to 50 mg/day for tolerability reasons at any time. Subjects who have a dose reduction for tolerability will continue to receive the reduced dose for the remainder of the study. The final dose, on Day 14, should occur approximately 2 to 4 hours prior to the final PET scan.

d The SCID-CT will be used to support the DSM-5 diagnosis and must be administered by a qualified rater with at least 2 years' experience with the population under study.

e Vital signs will include supine and standing measurements of blood pressure and heart rate, respiratory rate, and oral body temperature.

f Subjects must be fasted (no food or drink except water at least 8 hours prior to specified blood tests). Blood samples should be drawn in the morning followed by a snack or meal.

g Blood samples for follicle stimulating hormone (FSH) will be collected if menopause is suspected.

h Any positive urine  $\beta$ -hCG test should be confirmed by a serum  $\beta$ -hCG test. Must be performed prior to PET scan on same day as screening scan and on Day 14 scan.

i Blood samples for determination of SEP-363856 and SEP-363854 concentrations will be collected on Day 1 (approximately 10 minutes prior to dosing), Day 2 (2 – 4 hours postdose), Day 7 (2 – 4 hours postdose), Day 14 (prior to PET scan), and at Follow-up.

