#### **11.9.4. Early Termination (ET)**

The following procedures will be at this visit:

- Collect concomitant medications.
- Physical examination
- Vital sign measurements
- Weight
- Perform ECG.
- Collect blood sample for clinical laboratory evaluation (hematology, chemistry, serum prolactin, and fasted glucose panel and lipid panel).
- Collect blood sample for determination of plasma SEP-363856 and SEP-363854 concentration.
- Collect blood sample for antipsychotic levels.
- Female subjects only, collect urine samples for pregnancy test (any positive test must be followed up with a serum  $\beta$ -hCG test).
- Collect urine sample for urine drug screen (UDS).
- Perform psychiatric assessments in the following order: PANSS, BNSS, MADRS, C-SSRS, CGI-S. (Only perform PANSS, BNSS, MADRS, CGI-S if early termination occurs prior to Day 14 PET/MR scan.)
- BARS
- AIMS
- SAS
- Collect adverse events
- Perform PET/MR Scan including fMRI (only perform if the subject terminates the study prior to the Day 14 PET/MR Scan).

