### **13.2. Clinical Assessments After Study Drug Discontinuation**

Subjects who have not received study drug will not be followed up on leaving the study.

For subjects who have received study drug and who prematurely discontinue from the study treatment (ie, do not complete all visits through Follow-up), every effort should be made to complete the final evaluation procedures, in accordance with the early termination (ET) visit described in [Section 11.9.4](#).

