### 7.4. WINDOWING CONVENTIONS

No visit windowing will be performed for this study.

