### **16.9. PHARMACOKINETIC ANALYSIS**

Plasma concentrations of SEP-363856 and its metabolite SEP-363854 will be summarized descriptively at each scheduled sample collection time point.

Plasma SEP-363856 and SEP-363854 concentrations that are below the limit of quantitation (BLQ) will be treated as zero for the computation of descriptive statistics. However, if there is at least one BLQ value for a time point, the geometric mean and geometric coefficient of variation% will not be calculated for that time point. Missing concentrations will not be imputed.

Descriptive statistics (n, mean, standard deviation, CV%, geometric mean, geometric coefficient of variation% [GCV%], median, minimum, maximum) will be used to summarize plasma SEP-363856 and SEP-363854 concentration data.

A subject listing of all plasma concentration-time data for SEP-363856 and SEP-363854 will be presented for all subjects enrolled.

Document:	\\quintiles.net\enterprise\Apps\sasdata\SASa\sas\Sunovion\S 363856\BZA44200\Biostatistics\Documentation\SAP\V1\SEF	8EP- 2 361-301 SAP Final ∖	/1.0_26JUL2023
Author:		Version Number:	Final 1.0
		Version Date:	26JUL2023
Template No.:	CS_TP_BS016 Revision 5	Reference: C	S_WI_BS005

Effective Date: 01Apr2018

Sumitomo Pharma PROTOCOL SEP361-118

Statistical Analysis Plan

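### SAP 7.3 maps early-termination PK samples into the Week 2 concentration summary with no check on time since last dose (minor)

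*SAP*

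**What the plan says.** **The mapping rule.** SAP 7.3 says, for by-visit summaries: "Early termination data will be mapped to the next scheduled or planned timepoint where an assessment is expected to be performed". It then fixes the scope: "This applies to all efficacy, safety, and PK data". SAP 7.4 adds: "No visit windowing will be performed for this study".

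**The PK summary.** SAP 16.9 summarises SEP-363856 and SEP-363854 concentrations at each scheduled sampling time. Its handling rules cover only missing values and values below the limit of quantitation (BLQ). A BLQ value counts as zero, and "if there is at least one BLQ value for a time point, the geometric mean and geometric coefficient of variation% will not be calculated". Nothing refers to time since last dose or to whether the subject was still on drug.

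**Scheduled samples are tied to dosing.** Table 2 footnote i of the protocol sets "Day 2 (2 – 4 hours postdose), Day 7 (2 – 4 hours postdose"), with Day 14 before the PET scan and a further sample at Follow-up. For Day 14 the Synopsis says: "The final dose, on Day 14, should occur approximately 2 to 4 hours prior to the final PET scan".

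**The ET sample is not tied to dosing.** Protocol 11.9.4 says only "Collect blood sample for determination of plasma SEP-363856 and SEP-363854 concentration". The sampling table in Protocol Appendix III has no ET row. Protocol 13.2 says that "every effort should be made to complete the final evaluation procedures, in accordance with the early termination (ET) visit", with no interval from the last dose.

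**Two related texts.** SAP Appendix 1 (Presentation of Visits) says that early termination is for listings only. Protocol 11.7 requires dose and sampling times to be recorded.

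**The concern.** Carrying an ET assessment forward to the next visit is a common convention for rating scales. A plasma concentration is different: its meaning depends on how long after a dose the blood was drawn. Under the rule as written, a concentration drawn at an unspecified time after the last dose joins values drawn at a set time after a dose, under one time-point label.

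An off-drug ET sample is a foreseen case. Protocol 10.3.1 asks for the scans to be completed even when study drug has been discontinued, and 11.9.4 places the PET scan in the ET visit for subjects who leave before the Day 14 scan.

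At stake is the readability of one descriptive table. Plasma concentration at each post-dose time point is listed among the other endpoints (SAP 3.3). The geometric mean and geometric CV (GCV%) are the sensitive statistics, because one very low value pulls on the log scale and one BLQ value removes both.

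**Working it through.** **Step 1: where an ET sample lands.**
- ET after Day 7 and before the Day 14 sample: Week 2. This route is direct.
- ET after the Day 2 sample and before Day 7: Day 7 if Table 2 footnote i is part of the schedule. Neither Table 2 nor the visit list in SAP Appendix 1 has a Day 7 column, so if only columns count, this sample also lands in Week 2.
- ET after Day 14: Follow-up, where off-drug levels are expected. This is not a problem.

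**Step 2: the number of subjects.** Protocol 15.1 plans 22 subjects, from 16 with complete PET scans and 25% drop-out: 16/(1 - 0.25) = 21.3, rounded up to 22. The figure reproduces and is used as n.

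**Step 3: assumptions.** The documents give no half-life, on-drug CV, quantitation limit or ET interval. I assume 21 scheduled values with mean 1 and sample CV 30%, plus one mapped ET value at a fraction f of the on-drug level. With h the number of half-lives past the scheduled sampling time, f = 0.5^h.

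**Step 4: formulas**, using the sample SD and the GCV% formula in SAP 7.6.
- Arithmetic mean ratio = (21 + f)/22.
- Geometric mean ratio = f^(1/22).
- GCV% = 100 × sqrt(exp(s²) - 1), where s² = [20 × ln(1.09) + (21/22) × (ln f)²]/21.

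**Step 5: example at h = 3 (f = 0.125).**
- Mean: 21.125/22 = 0.960.
- Geometric mean: 0.125^(1/22) = 0.910.
- s² = (20 × 0.0862 + 0.9545 × 4.324)/21 = (1.724 + 4.128)/21 = 0.279, so GCV% = 56.7%.

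| ET value | Mean ratio | Geometric mean ratio | GCV% |
|---|---|---|---|
| No ET value (21 scheduled) | 1.000 | 1.000 | 30.0 |
| f = 1 (on-drug level) | 1.000 | 1.000 | 29.2 |
| f = 0.5 (h = 1) | 0.977 | 0.969 | 33.1 |
| f = 0.25 (h = 2) | 0.966 | 0.939 | 43.0 |
| f = 0.125 (h = 3) | 0.960 | 0.910 | 56.7 |
| BLQ, counted as 0 | 0.955 | not calculated | not calculated |

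**Step 6: sensitivity.** At h = 3, GCV% is 51.3% if the on-drug CV is 20% and 71.1% if it is 50%. With two mapped values at zero the arithmetic mean ratio is 20/22 = 0.909.

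**The case against.** **Impact is small.** This stands. The endpoint is descriptive, SAP 16.9 also reports the median, and every value remains in the listings. No test or decision rests on the table.

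**SAP Appendix 1 confines early termination to listings.** This could mean that ET data stay out of tables. The more natural reading is that ET is not a table heading because the data have been remapped; SAP 15.2 supports this by defining the Week 2 efficacy record as Day 14 or ET. On the other reading, Appendix 1 contradicts SAP 7.3. Either way the two need reconciling.

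**The Day 7 route is uncertain.** This stands, and the point is limited accordingly. The Week 2 route does not depend on it.

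**The larger effects rest on assumed inputs.** This stands. Dosing is in-clinic, and an ET sample close to the scheduled post-dose time would change almost nothing. The documents show that an off-drug value can enter, not that it is likely.

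**Removing ET mapping is not enough.** This stands. Protocol 17.3 says that stopping study medication does not necessarily end participation, so a subject could reach Day 14 off drug and enter Week 2 as a nominal value. The fix has to cover that case.

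**Stronger readings a reader might infer.** One is that the 25% drop-out allowance implies five or six near-zero values in one summary. The documents do not support this: the allowance concerns complete PET scans and says nothing about ET timing or concentrations. Another is that the primary result is compromised. The PET analysis falls under a separate SAP, and population PK is reported separately; this rule governs neither.

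**Conclusion.** The point holds as a minor one. Applied as written, SAP 7.3 with 7.4 and 16.9 allows an ET concentration of unspecified time since dose into the Week 2 summary, and into Day 7 if footnote i counts as schedule.

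For one mapped value among 22 at an assumed on-drug CV of 30%, the arithmetic mean moves 0 to -4.5%. The geometric statistics are more exposed: at three half-lives past the scheduled time the geometric mean falls 9.0% and GCV% goes from 30% to about 57%, and both are lost if the value is BLQ. These figures illustrate the mechanism and do not predict what will happen.

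The listings, primary PET analysis, sample size, power and population PK work are unaffected.

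**What to change.** 1. **SAP 7.3:** remove PK from the ET mapping. Show ET concentrations in listings only, with time since last dose derived from the recorded times.
2. **SAP 16.9:** apply the same rule to a nominal-visit sample taken after study drug was discontinued early. List and flag it, and leave it out of the on-drug summary and so out of the BLQ rule for that time point. Scheduled Follow-up samples are off drug by design and stay in their own summary.
3. **SAP 7.3 and Appendix 1:** state whether ET data appear in tables, by data type, so that the two sections agree.
4. **Protocol:** reconcile the Day 2 and Day 7 sampling time. The Synopsis and Section 7.1 place it at about the time of dosing; Table 2 footnote i and Appendix III place it 2 to 4 hours after the dose.

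Items 1 to 3 are SAP wording and programming and need no new data. Item 4 is a protocol clarification. The statistical cost is one fewer value per ET subject at the affected time point, for example 21 instead of 22.
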